The process of desensitization through immunotherapy occurs after an initial food challenge to determine what amount of food allergen causes a clinical reaction in the subject. There are two phases in treatment with oral immunotherapy. In the first phase, the build-up phase, the subject ingests gradually escalating doses of peanut flour, administered orally in a vehicle once every day with weekly or bi-weekly dose escalation. Once a maintenance dose has been achieved, the subject continues to take this amount in a peanut equivalent dose over a period of years. Peanut equivalent dosing has been used in several prior peanut OIT trials without report of increased side effects or adverse events. (17-20) The peanut flour manufacturer for the initial trials in peanut oral immunotherapy by centers in the Consortium of Food Allergy Research (CoFAR) only provided dosing for the buildup phase for the trials and peanut equivalent dosing was used by centers for the maintenance phase. (Personal communication) Therefore, given the experience with peanut equivalent dosing, after the first year of this study, patients will be switched to a daily peanut equivalent dose and intake will be monitored by daily diaries. Since the daily dose will still be 3900 mg of peanut protein for the maintenance phase, the immunologic effects of the peanut dosing are not likely to be affected. (11, 12)

An open label study with an initial dose of 100 µg increased to 300 mg maintenance dose for several months demonstrated efficacy in over 90% of the subjects with desensitization and tolerance of a 3900 mg dose on food challenge.(11,12) A follow up double blind study

demonstrated efficacy with treated subjects tolerating 5000 mg compared to 280 mg in placebo subjects. The safety analysis of these studies demonstrated that 93% of children experienced symptoms on initial dosing day with 15% requiring epinephrine.(9) Most reactions were mild. However, when the initial dose was decreased from 50 mg down to 6 mg, allergic side effects were noted in only 47%. Of 10,184 home maintenance dosings of peanut flour, only 3.5% caused symptoms, with 2 subjects receiving epinephrine, each after one maintenance dose (0.02%). The relative safety of this approach has been demonstrated in these initial trials.(9)

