The CAGT is a Good Manufacturing Practice (GMP) compliant facility (See Letter of Authorization) and is accredited by the Foundation for the Accreditation of Cellular Therapy (FACT), the College of American Pathologists (CAP) and is CLIA registered. The protein doses will be monitored and dispensed by the CAGT GMP Facility.

The drug would be stored in the cold room (2-8°C) within the clean room area restricted to CAGT GMP Facility Staff. It is on continuous temperature monitoring via our Isensix system. In the case of an alarm staff is informed via pager system. Alarms and monitoring data are also full backed up by Isensix in San Diego. This drug will be stored in a dedicated facility away from other allergens and will be handled in a separate room on a separate air handling systems.

The pre-measured soufflé cups will be transported by a clinical research staff member within Texas Children's Hospital controlled environment.

The peanut flour will be used within the manufacturer's expiry date and our center will follow all instructions provided by the manufacturer.

One dose of peanut flour is taken per day. Prior to taking the dose the subject must eat a snack high in carbohydrate and fat such as a bagel or chips and then eat the peanut flour mixed into liquid or another food such as apple sauce or ice cream.

The vehicle food for each subject will be a food, to which the subject is not allergic. The subject will need to eat the peanut flour at approximately the same time every day. After eating the peanut flour the subject will need to be with a supervising adult for the next 2 hours so they can monitor for any possible reaction. The subject cannot go to school within 2 hours of eating the

peanut flour and cannot go to bed within 2 hours of eating the peanut flour. After 1 month, if there are no adverse events with the maintenance dose or highest dose tolerated, the provider will have the option of decreasing the observation period to 1 hour with no physical activity to occur for 1 hour.

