No subject initiating therapy in this trial will be replaced. The stopping rules for individual subjects are as follows:

- Greater than or equal to four missed or 'no-show' appointments and four missed home doses,
- Greater than 4 instances of not having or carrying an unexpired epinephrine injector to appointments
- Anaphylactic reaction listed as a Grade 4 as defined by the World Allergy Organization grading scale for systemic reactions to immunotherapy related to peanut OIT dosing at any stage of the protocol.
- Any participant is diagnosed with eosinophilic esophagitis
- Any participant is diagnosed with moderate to severe asthma based on the NHLBI guidelines
- Any participant needs treatment with greater than medium daily doses of inhaled corticosteroids, as defined by the NHLBI guidelines
- Any participant has an accidental peanut ingestion with anaphylaxis during the time on oral desensitization

Participants may be prematurely terminated from the study if:

- The participant elects to withdraw consent from all future study activities, including follow-up
- The participant is “lost to follow-up” (i.e., no further follow-up is possible because attempts to reestablish contact with the participant have failed)
- The participant dies

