9. MEASUREMENT OF EFFECT

9.1. Response Review:

The Data Safety Monitoring Committee will review the responses to the primary and secondary objectives every 6 months during the trial.

9.2. Response Criteria:

9.2.1. The primary objective will be measured by recording the daily symptoms experienced by the subjects and the number of subjects with no clinical symptoms during 6 g peanut flour challenge at time 50 weeks compared to time 0 weeks. The change in tolerated dose will be assessed between baseline and one year. The proportion of patients who tolerate 6 g of peanut flour will be compared at baseline and at the one year point using McNemar's test for matched pair data. The proportion of subjects will be estimated with exact binomial confidence intervals.

9.2.2. For the first secondary objective, flow cytometric analysis of T, NKT cells, and basophils will be performed through the measurement of the percent of cells producing a

cytokine as well as measuring surface and intracellular markers expressed upon activation and the significance of changes from time 0 to 1 year will be assessed as described below by using a paired t-test of the log-transformed data. Baseline measures of cell activation will be summarized by means with standard deviation. Normality will be assessed by quantile-quantile plots, and non-normality will be addressed by data transformations. A general linear mixed model will be used to estimate the effect of the therapeutic procedure over time. The model will include a fixed effect for time (discrete), and the matrix of correlated error terms will assume a first-order autoregressive structure. Alternative correlation structures such as the unstructured and compound symmetry will be considered. Correlation structures will be assessed by Akaike's Information Criteria. The likelihood ratio test will be used to test for overall significance of the model. P-values will be adjusted using the Holm's step down Bonferonni correction for multiple comparisons. Activation responses that are significant at the 0.05 level after adjustment will be further assessed. Pairwise comparisons between discrete time points will be tested for significant differences, and p-values will be adjusted using the Bonferonni correction. Statistical significance of the adjusted p-values will be assessed at the 0.05 level.

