Spearman rank correlations will be estimated for all pairwise comparisons between activation responses. P-values for testing for significant correlations will be adjusted using Bonferonni's correction for multiple comparisons. Partial correlation coefficients will also be estimated for all activation responses adjusting for subject-level effects across all time points.

- 9.2.3. The second secondary objective will be assessed by recording the number of episodes of prior viral infection symptoms experienced after symptomatic daily peanut dosing. This number will be compared to the episodes of symptomatic daily peanut dosing with no prior viral infection symptoms. The proportion of subjects will be estimated with exact binomial confidence intervals. This analysis will also be used to determine the proportion of symptomatic daily doses with preceding symptoms of viral infection compared to non-viral associated symptomatic daily doses.
- 9.2.4. The third secondary objective will be assessed by the comparison of amount of peanut protein tolerated at the 24 month food challenge to the 25 month food challenge using McNemar's test for matched pair data.

[figure not shown]

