10. STATISTICAL CONSIDERATIONS

10.1. *Sample size considerations:*

Sample size was estimated to detect a statistically significant difference in the proportion of T cells producing interferon-gamma (IFN gamma), at the 1 year time point compared with baseline using a paired t-test. A difference in proportions of 0.60 units (.2 at baseline and .8 at 1 year) would be clinically important. Assuming a common SD=0.6 at each time point, correlation between repeated measures is 0.50 and alpha = 0.05, a sample size of 10 subjects would be required to detect this difference with 80% power. Assuming 50% attrition, this study will plan to enroll a total of 15 subjects.

Notes:

- 13 subjects for 90% power with alpha=0.01
- 16 subjects for 80% power with alpha=0.01
- 19 subjects for 90% power with alpha=0.01

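### Section 9.2.3 carries an exact binomial interval over from children to daily doses, with no allowance for repeated doses within a child

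*Combined protocol and SAP*

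**What the plan says.** Section 9.2.3 covers the second secondary objective, on viral symptoms and reactions to dosing. It first compares counts of episodes, with and without prior viral symptoms. It then names its only interval: "The proportion of subjects will be estimated with exact binomial confidence intervals". The next sentence moves to another unit: "This analysis will also be used to determine the proportion of symptomatic daily doses with preceding symptoms of viral infection", compared with symptomatic doses not linked to viral symptoms. No other method is given for that proportion, and no confidence level is stated.

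The doses are repeated measures. Section 6.2 says "One dose of peanut flour is taken per day", and Section 2.1.1 describes a 50-week escalation followed by 104 weeks of maintenance. The number of children is small and fixed. Section 10.1 says "Assuming 50% attrition, this study will plan to enroll a total of 15 subjects", and Section 6.11 says "No subject initiating therapy in this trial will be replaced".

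Section 9.2.2 does allow for repeated measures in the cell-activation data. It uses a mixed model with correlated errors, and partial correlations adjusted for the subject.

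**The concern.** An exact binomial interval is valid when each unit is an independent trial. Children can reasonably be treated that way. Daily doses within one child cannot. Children differ in how reactive they are and how often they have colds, and one viral illness can precede several symptomatic doses in the same child. Pooling all symptomatic doses and treating them as independent overstates the information in the data. A few cold-prone or reactive children could then produce what looks like a precisely estimated viral share.

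**Working it through.** **The plan's own figure.** Section 9.2.3 gives no dose count, precision or coverage to reproduce. The plan's one calculation, 10 subjects for a paired t-test in Section 10.1, does reproduce at two-sided 0.05 (power 0.803), but it does not bear on this interval.

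**Inputs from the documents**
- Children: 15 enrolled (10.1). With the stated 50% attrition, 15 × 0.5 = 7.5 complete.
- Doses per completer: (50 + 104) weeks × 7 = 1,078 (2.1.1, 6.2).
- Share of doses with symptoms: 3.5%, from an earlier study described in Section 1: "Of 10,184 home maintenance dosings of peanut flour, only 3.5% caused symptoms".

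**Assumptions, not in the documents**
- The 3.5% rate carries over to this trial's build-up and maintenance doses.
- The level is 95%. The nearest support is the 0.05 level in 9.2.2: "Statistical significance of the adjusted p-values will be assessed at the 0.05 level".
- The true viral share is p = 0.30.
- The ICC lies between 0.01 and 0.20.
- Counts per child are either equal or have a coefficient of variation (CV) of 1.

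**Step 1: number of symptomatic doses.** Per completer, 1,078 × 0.035 = 37.7, or about 38. For 15 children, 15 × 38 = 570. For 7.5 completers, 7.5 × 37.7 = 283. As a low-count case I use 7 per child (about 100 in all), a symptomatic rate of 7/1,078 = 0.65%.

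**Step 2: what each ICC means.** The SD of the children's true viral shares is √(ICC × p(1−p)), with p(1−p) = 0.21. At ICC 0.01 this is √0.0021 = 0.046. At 0.05 it is √0.0105 = 0.10. At 0.10 it is √0.021 = 0.145. At 0.20 it is √0.042 = 0.205.

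**Step 3: loss of information.** The design effect is DEFF = 1 + ((1 + CV²)m − 1) × ICC, with m the mean count per child. The effective number of doses is the total divided by DEFF. For m = 38 and ICC 0.10:
- equal counts: 1 + 37 × 0.10 = 4.70, and 570/4.70 = 121
- CV = 1: 1 + 75 × 0.10 = 8.50, and 570/8.50 = 67

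Approximate coverage is 2Φ(1.96/√DEFF) − 1, which gives 63% and 50%.

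**Step 4: simulated coverage of the nominal 95% exact interval.** The model is beta-binomial by child, with 15 children and p = 0.30. Entries are equal counts / CV = 1. Repeat runs agree to within about 2 percentage points.

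| ICC | about 38 per child | about 7 per child |
|---|---|---|
| 0.01 | 91% / 87% | 95% / 95% |
| 0.05 | 76% / 65% | 91% / 88% |
| 0.10 | 65% / 52% | 89% / 83% |
| 0.20 | 52% / 41% | not needed for the conclusion |

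Fewer children with the same count each do not help, because DEFF depends on the count per child. With 285 doses in 8 children, coverage is 79%/68% at ICC 0.05 and 66%/56% at 0.10.

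**Step 5: the alternative.** This is a ratio estimator with child-level variance and t on (children − 1) degrees of freedom. At 570 doses, 15 children and ICC 0.10, its half-width is about 0.09 (equal) to 0.10 (CV = 1), against about 0.04 for the exact interval. Its coverage is 95% (equal) or 90% (CV = 1). With 8 to 15 children of very unequal size it covers only about 85–92%.

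**The case against.** The strongest reply is textual. The sentence that names the interval speaks of subjects, and for children the method is correct. Dose-level use rests on the follow-on sentence, which could be read as carrying over only the counting and comparison. That stands as a caution. But if a per-child proportion was meant, the text has to say so, and the same edit is needed.

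The second reply concerns size. A reader might infer that hundreds of symptomatic doses are certain and that the interval covers far less than 95%. The documents support neither as fact. The 3.5% rate comes from home maintenance doses in another study, half the children may leave, and build-up is shorter for children who start at a higher dose. If 9.2.3 means episodes that each span several doses, there are fewer units again. At ICC 0.01, or with few doses per child, coverage is close to nominal.

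The third reply concerns scope. A reader might extend the point to the primary outcome, because Section 9.2.1 says "The primary objective will be measured by recording the daily symptoms experienced by the subjects". But 9.2.1 uses the exact interval only for the proportion of children tolerating the challenge, which is correct use. It plans no interval for daily-symptom rates, so there is none to fault.

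Finally, this is a secondary estimate. Section 9.2.3 attaches no p-value, threshold or decision rule to it, and neither the sample size nor the stopping rules use it. That limits the severity.

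**Conclusion.** The point holds for Section 9.2.3, on the natural reading of its text. The direction is certain: any positive within-child correlation makes a dose-level exact binomial interval too narrow, and nothing in the documents corrects for it. The size is conditional on an assumed 95% level, a 30% viral share, the ICC and the number of symptomatic doses per child. Across the cases shown, coverage runs from nominal (95% at ICC 0.01 with about 7 doses per child) to about 41% (ICC 0.20, about 38 per child, unequal counts). The loss becomes serious from an ICC of about 0.05 when each child contributes dozens of symptomatic doses. Severity: SHOULD-FIX.

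**What to change.** Amend Section 9.2.3 only:

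1. State the unit (child, episode or dose) for each proportion.
2. Keep the exact binomial interval for proportions of children, and state its level.
3. For proportions of doses or episodes, take the child as the unit. Use a ratio estimator with child-level variance and t on (number of contributing children − 1) degrees of freedom, or a bootstrap that resamples children. Only the t-based version was checked here, so the bootstrap should not be presumed to do better with so few children.
4. Report each child's count of symptomatic doses and how many had preceding viral symptoms.
5. Label the dose-level result descriptive, since the child-level interval also falls short of nominal when few children contribute very unequal counts.

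The cost is a few sentences and wider intervals: roughly ±0.09 to ±0.10 instead of ±0.04 in the ICC 0.10, 570-dose case. No new data are needed, because the daily symptom diaries (8.1.3) are already kept by child.

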2. OBJECTIVES

2.1 *Primary Objectives:*

- 2.1.1. The primary objective is to determine whether peanut oral immunotherapy safely develops clinical tolerance in peanut allergic patients by assessing the change of dose tolerated and to determine the percentage of subjects who can tolerate 6 g of peanut flour with absence of clinical symptoms during a food challenge following the initial desensitization phase of peanut flour which includes a 50 week dose escalation phase and 104 week maintenance phase on a peanut equivalent dose.

2.1. Secondary Objectives:

To determine the immune mechanisms of clinical tolerance, using technology to identify T cell cytokine responses and subsets, as well as basophil activation responses as measured by flow cytometry. T and NKT cell function and intracellular cytokine expression will be measured.

2.2.1. To determine whether viral exposure potentiates response to in vitro peanut allergen exposure and to assess those changes during peanut OIT.

2.2.2. To compare the change in dose tolerated after one month of abstaining from peanut to determine sustained unresponsiveness.

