The DBPCFC visit will last approximately 9 hours. The food challenge may be performed in one day or split into two days. The subject will discontinue antihistamines (for example Zyrtec or Claritin) for 7 days before the procedure and must be off oral corticosteroids for one month before the food challenge.

Peanut equivalent will be used for the food challenge. The challenge will consist of increasing doses of peanut (in the form of peanut flour and mixed with juice or baby food) given every 15 minutes in increasing amounts (Table 6). The other challenge will consist of placebo material given also in increasing doses. The highest dose of peanut flour will be equivalent to approximately 34 peanuts.

They will return 4 weeks after the 24 month food challenge for the 25 month food challenge. It will be conducted in the same manner as the 24 month food challenge. During this 4 week interval the subject must avoid peanut in his or her diet and will not take any peanut protein as he or she had been doing previously.

- Review Home Symptom Diary: At the 24 month visit we will review any symptoms experienced while taking the food protein.
- Urine Pregnancy Test: For females of reproductive potential a urine pregnancy test will be performed prior to the food challenge at both the 24 month and 25 month visits. If the subject is pregnant the food challenge will not be performed and the subject will be dismissed from the study.

Table 6.

24 and 25 Month Maintenance Phase Double-Blinded Placebo Controlled Food Challenge Protocol
--

Dose Number	Approximate Dose Weight (PEANUT PROTEIN)	Cumulative Dose Weight (peanut protein)
1	75 mg	75 mg
2	150 mg	225 mg
3	500 mg	725 mg
4	1000 mg	1725 mg
5	2000 mg	3725 mg
6	3000 mg	6725 mg
7	4000 mg	10725 mg
8	4500 mg	15225 mg
9	5000 mg	20225 mg
10	6000 mg	26225 mg

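### Section 9.2.4 applies McNemar's test, which needs a paired yes/no outcome, to the amount of peanut protein tolerated at months 24 and 25, and its text gives no cut-off

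*Combined protocol and SAP*

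**What the plan says.** The objective in Section 2.2.2 is worded as a change in dose: "To compare the change in dose tolerated after one month of abstaining from peanut to determine sustained unresponsiveness". Section 9.2.4 assigns the analysis: "comparison of amount of peanut protein tolerated at the 24 month food challenge to the 25 month food challenge using McNemar's test".

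The outcome comes from the challenge in Section 6.7. Table 6 has ten ordered doses, from 75 mg to 6000 mg of peanut protein, and the same series is given at both visits. Section 6.7 describes the purpose of these challenges as finding out whether the child remains allergic or can now tolerate peanut.

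The plan uses McNemar's test once more, in Section 9.2.1, and there it has a yes/no outcome: the "proportion of patients who tolerate 6 g of peanut flour will be compared at baseline and at the one year point". The underlying criterion in Section 2.1.1 is the "percentage of subjects who can tolerate 6 g of peanut flour with absence of clinical symptoms during a food challenge", placed after a "50 week dose escalation phase and 104 week maintenance phase on a peanut equivalent dose".

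**The concern.** McNemar's test compares two paired proportions. It uses only the subjects who change from yes to no or from no to yes. It cannot be run on a tolerated amount until someone decides which amounts count as yes, and 9.2.4 does not say.

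Three things follow once a cut is imposed:
- A change in dose that does not cross the cut counts as no change.
- The result can depend on which cut is used.
- With no cut written down, it could be chosen after the challenge results are known.

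This is the plan's only stated analysis of sustained unresponsiveness. The defect lies in the analysis text alone, because the tolerated doses are recorded at both challenges.

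**Working it through.** **No stated figure to reproduce.** The plan gives no sample size or power for month 24 versus month 25. Section 10.1 sizes the study on a different endpoint (T cells producing interferon-gamma, 10 subjects) and then says "Assuming 50% attrition, this study will plan to enroll a total of 15 subjects". That suggests roughly 15 × 0.5 = 7.5, so 7 or 8 pairs, or 10 if the Section 10.1 requirement is met. I assume 7 to 10 pairs.

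**Where a borrowed 6 g criterion would fall in Table 6.**
- Table 3 pairs 6000 mg flour with 3000 mg protein (2:1). Taken literally, 6 g flour is 3000 mg protein, which is dose 6 of Table 6.
- Table 6 is in protein and ends at 6000 mg. If 6 g protein was meant, the cut is dose 10.
- Section 6.7 mixes the units: "The highest dose of peanut flour will be equivalent to approximately 34 peanuts". At 0.175 g protein per peanut (Table 4), 34 × 0.175 = 5.95 g, which matches the top dose in protein, not in flour.

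The documents therefore leave two candidate cuts, dose 6 and dose 10.

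**Does the choice matter?** I constructed two sets of 8 subjects to show what can happen. They are not forecasts. Yes means the highest tolerated dose is at or above the cut. Exact two-sided McNemar with k discordant pairs, all in one direction, gives P = 2/2^k, capped at 1.

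| Set | Month 24 (Table 6 dose) | Month 25 | Discordant at dose 6 | P | Discordant at dose 10 | P |
|---|---|---|---|---|---|---|
| 1 | all 10 | 9, 9, 8, 8, 7, 7, 6, 6 | 0 | 1.0 | 8 | 2/256 = 0.008 |
| 2 | 7, 7, 8, 8, 9, 9, 10, 10 | 6, 6, 6, 7, 7, 8, 8, 9 | 0 | 1.0 | 2 | 2/4 = 0.5 |

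All 8 subjects decline in both sets, so the exact signed-rank test and the exact sign test each give 2/2^8 = 0.008 in both. A subject who falls from dose 10 to dose 6 goes from 6000 to 3000 mg, a loss of (6000 − 3000)/6000 = 50%, and counts as unchanged at a dose-6 cut.

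**Is signed-rank free of choices?** No. It ranks the sizes of the changes, and Table 6 doses are unevenly spaced (75 mg between doses 1 and 2, 1000 mg between doses 9 and 10). Take month-24 doses 4, 5, 4, 9, 3, 3, 9, 7 and month-25 doses 2, 3, 2, 10, 1, 1, 6, 8, a set searched for to show the point:
- In steps, the two increases rank 1.5 and 1.5 (sum 3 of 36), and exact P = 8/256 = 0.031.
- In mg of highest single dose, the changes are −850, −1500, −850, +1000, −425, −425, −2000 and +500. The increases rank 6 and 3 (sum 9), and exact P = 64/256 = 0.25.
- The sign test has 6 falls and 2 rises on either scale: P = 2 × (28 + 8 + 1)/256 = 0.29.

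The scale must therefore be fixed in advance, or a test that ignores it must be used.

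**Smallest informative number.** Five changes in one direction give 2/2^5 = 0.063, and six give 2/2^6 = 0.031. The exact signed-rank, sign and McNemar tests share this floor.

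**The case against.** The strongest reply is that the authors meant a yes/no outcome and wrote amount loosely. Section 6.7 frames the challenge as allergic or tolerant, Section 2.2.2 refers to sustained unresponsiveness, and Section 2.1.1 places the 6 g criterion after the 104-week maintenance phase. On that reading McNemar is a suitable test. This stands as a plausible account of intent, but it does not complete the plan. Section 9.2.4 says amount, Section 2.2.2 says change in dose, Section 9.2.1 applies the 6 g flour criterion only to baseline versus one year, and the flour/protein conflict leaves two cuts.

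A second reply also stands: the ambiguity should not be inflated. A reader might infer further cuts from the cumulative column of Table 6. The entry challenge, called a 1 gram challenge, is named by its single top dose (1000 mg in Table 2, against a cumulative 2000.5 mg), so the cumulative readings have little support.

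Third, the constructed sets keep every subject at dose 6 or above, so no discordance at dose 6 is possible. They show that the cut can decide the result, not that it will.

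Finally, the figure after 9.2.4 is not shown, so the finding covers the text only.

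**Conclusion.** The concern holds as stated. The test named in 9.2.4 cannot be run on the endpoint named there, and the yes/no endpoint that would make it usable is not defined in the text. Between the two cuts the documents could support, the same constructed data give P = 1.0 or P = 0.008.

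Two stronger readings are not supported. A reader might infer that McNemar is wrong for this objective under any definition. It is not: with a yes/no endpoint fixed beforehand it is appropriate. A reader might also infer that McNemar is always the weaker test here. That depends on distributions the documents do not give, and power is not the basis of this point.

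This is one secondary objective in a planned 15-subject study that was not sized for it, and no data are lost. The conclusion rests on the text shown and on the 2:1 flour-to-protein ratio of Tables 2 and 3. The remark about 7 to 10 pairs rests on the Section 10.1 attrition figure.

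**What to change.** Rewrite Section 9.2.4 before the month-24/25 data are analysed:

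- Analyse the amount in subjects with both challenges, using a two-sided paired test for an ordered outcome. Either use an exact Wilcoxon signed-rank test on the highest tolerated dose, with the scale fixed in advance (mg of highest single dose, or Table 6 step) and the handling of ties and zero changes stated, or use an exact sign test, which does not depend on the scale.
- Report the median paired change in mg, the number of zero changes, and the number of subjects at the top dose at each visit.
- If a yes/no sustained-unresponsiveness endpoint is also wanted, define it separately, reconcile the flour and protein wording first, and use exact McNemar for that endpoint only.
- State that with about 7 to 10 pairs each of these exact tests needs at least 6 non-zero changes or discordant pairs to reach P < 0.05.

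The cost is one paragraph and a slightly larger analysis. No visit, procedure or data item is added, because the same ten-dose challenge is already given at both visits.

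### The Month 24 versus Month 25 McNemar test in 9.2.4 can show loss of tolerance but cannot establish sustained unresponsiveness, and no estimate or interval is planned for that objective

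*Combined protocol and SAP*

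**What the plan says.** The last secondary objective (section 2, item 2.2.2) reads "To compare the change in dose tolerated after one month of abstaining from peanut to determine sustained unresponsiveness". Section 6.7 supplies the design: a food challenge at Month 24, a second one four weeks later, and, in between, "During this 4 week interval the subject must avoid peanut in his or her diet". Both challenges follow the ten dose steps of Table 6.

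Section 9.2.4 holds the whole analysis, described as "comparison of amount of peanut protein tolerated at the 24 month food challenge to the 25 month food challenge using McNemar's test for matched pair". It gives no cut-off that turns an amount into pass or fail, and no definition of sustained unresponsiveness in a child. It also gives no retained proportion, interval, significance level or version of the test. Exact binomial intervals for a proportion are planned in 9.2.1 and 9.2.3, but not here.

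On numbers, section 10.1 states "Assuming 50% attrition, this study will plan to enroll a total of 15 subjects", and section 6.11 adds "No subject initiating therapy in this trial will be replaced". The sample size in 10.1 is for a one-year interferon-gamma comparison. None is given for Month 24 against Month 25.

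**The concern.** Sustained unresponsiveness means that tolerance is still there after the break. McNemar's test takes no net change as its null hypothesis, so the state of interest is the one the test assumes and can only reject. Rejection would show that tolerance was lost. Failure to reject, in a study this small, is compatible with anything from no loss to a large loss. Neither result answers the objective.

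The test also needs a binary outcome, while 9.2.4 applies it to an amount. A sign or signed-rank test on the doses would cure that mismatch, but it would keep the same null hypothesis and so the same limitation.

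Month 25 is the only challenge in the protocol that follows a period off peanut. Section 1 separates tolerance after stopping daily dosing from desensitisation during dosing, and section 11 names becoming tolerant as a possible benefit. This comparison is therefore the trial's only clinical evidence on that benefit. A bare statement of no significant change could be taken for persistence by families or by those planning later trials.

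**Working it through.** **1. The plan's own sample size.** Section 10.1 states "Assuming a common SD=0.6 at each time point, correlation between repeated measures is 0.50 and alpha = 0.05" and a difference of 0.60. The SD of the paired difference is √(2 × 0.6² × (1 − 0.5)) = 0.6, so the standardised effect is 0.6/0.6 = 1. A two-sided paired t-test at 0.05 (noncentral t) then needs 10 subjects (power 0.803), so the stated 10 reproduces. It has no bearing on 9.2.4.

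**2. How many pairs.** Fifty per cent attrition from 15 leaves 15 × 0.5 = 7.5, that is 7 or 8. But 15 is also 10 × 1.5, which suggests a target of 10 evaluable children. The maximum is 15. I therefore show 7 to 15.

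**3. Assumptions not in the documents.** Two-sided level 0.05; a pass/fail cut-off exists; all completers pass at Month 24; no child gains tolerance during avoidance.

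**4. Cut-off of the test.** With b losses and no gains:

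- Exact: p = 2 × 0.5^b. Five losses give 0.0625 and six give 0.031.
- Continuity-corrected chi-square, (b − 1)²/b: five give 16/5 = 3.2, p = 0.074; six give 25/6 = 4.17, p = 0.041.
- Uncorrected chi-square, b²/b = b: three give p = 0.083; four give p = 0.0455.

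So up to 5 losses are non-significant on the exact or corrected test, and up to 3 on the uncorrected test.

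**5. What 5 losses amount to**, with the Clopper-Pearson 95% interval for the proportion retained:

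| Pairs | Lost (exact or corrected limit) | Retained (95% CI) | Lost (uncorrected limit) |
|---|---|---|---|
| 7 | 5/7 = 71% | 29% (4% to 71%) | 3/7 = 43% |
| 8 | 5/8 = 63% | 38% (9% to 76%) | 3/8 = 38% |
| 9 | 5/9 = 56% | 44% (14% to 79%) | 3/9 = 33% |
| 10 | 5/10 = 50% | 50% (19% to 81%) | 3/10 = 30% |
| 15 | 5/15 = 33% | 67% (38% to 88%) | 3/15 = 20% |

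**6. Chance of a non-significant result** for a true loss rate q: P(Bin(n, q) ≤ 5) for the exact test and P(Bin(n, q) ≤ 3) for the uncorrected test.

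| Pairs | Exact, q = 0.5 | Exact, q = 0.6 | Uncorrected, q = 0.5 | Uncorrected, q = 0.6 |
|---|---|---|---|---|
| 7 | 0.938 | 0.841 | 0.500 | 0.290 |
| 8 | 0.855 | 0.685 | 0.363 | 0.174 |
| 10 | 0.623 | 0.367 | 0.172 | 0.055 |
| 15 | 0.151 | 0.034 | 0.018 | 0.002 |

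**7. If not every completer passes at Month 24.** Only Month 24 passers can become losses. With 5 or fewer passers and no gains, the smallest possible exact p is 0.0625, so the test cannot reject even if every one of them loses tolerance. Sections 6.4 and 6.5 and Appendix II allow children to be maintained below the full dose, so some completers may not pass. Gains raise the limit further: with 1 gain, 7 losses are non-significant (p = 0.070).

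**The case against.** The other side has real points.

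- Nothing in the documents says that a non-significant result will be called sustained unresponsiveness. A reader might infer such a rule from the wording of 2.2.2, but it is not written. Section 1 in fact expects oral immunotherapy not to produce tolerance once dosing stops, and on that expectation a test for loss is coherent. This stands. What remains is that the objective is to determine persistence and the plan offers nothing else from which to judge it.
- A reader might also infer that most children could lose tolerance unnoticed at any size from 7 to 15. That does not hold. With all completers passing and no gains, an observed majority loss is non-significant only at 7 to 9 pairs on the exact or corrected test. On the uncorrected chi-square it is always significant from 7 to 15 pairs. Section 9.2.4 does not name the version.
- If 10 evaluable children is the real target, 5 losses are half, not a majority. The attrition figure also belongs to a one-year comparison; the documents give none for Month 25.
- The losses counted above need a cut-off that 9.2.4 lacks. If doses are compared directly, partial losses count too, and the result for 5 or fewer passers does not carry over.
- No treatment decision hangs on this p-value. The exit dose in 6.8 rests on clinical judgment, and this is a secondary objective of a small uncontrolled study.

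These points limit the size and consequence of the problem. They do not give 9.2.4 a way to show persistence.

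**Conclusion.** The point holds in a limited form. As written, 9.2.4 cannot establish what 2.2.2 asks for, whichever version of the test is used and however many children complete. The figures are conditional on the assumptions in step 3. At the 7 or 8 children that 50% attrition from 15 implies, and at 9, the exact or corrected test can leave an observed majority loss non-significant. At 10 to 15 it cannot, unless some completers fail at Month 24 or some gain tolerance. The documents do not support the stronger claim that the plan will declare sustained unresponsiveness from a non-significant test; they leave that misreading open. This is a cheap improvement that should be made for a secondary objective, and it does not threaten the trial's main results.

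**What to change.** In 9.2.4:

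1. Make the main result for 2.2.2 the proportion of children passing a pre-stated challenge step at Month 24 who also pass that step at Month 25, with an exact 95% interval as already used in 9.2.1 and 9.2.3. The investigators should choose the step and write it down before the data are seen.
2. List every child's tolerated dose at both challenges, including children who did not pass at Month 24, because 2.2.2 concerns change in dose and the proportion leaves them out.
3. Keep the paired test as descriptive, name its version and level, and state that a non-significant result is not evidence of sustained unresponsiveness.
4. A threshold for a group-level claim is optional. If one is used, fix it in advance and compare it with the lower confidence limit.

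The cost is a few sentences, with no new visits, data or children. The downside is a wide interval and a more modest conclusion. Even 8 of 8 retained gives a lower limit of 0.025^(1/8) = 63%, and 15 of 15 gives 0.025^(1/15) = 78%. For 3 of 8 the interval is 9% to 76%, which tells the reader far more than p = 0.0625.
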